1.0 Study Summary

| | |
|--|---|
| Study Title: | PIVOTAL Pilot Study |
| Study Design: | Randomized + Prospective |
| Primary Objective | Collect preliminary data to be used for a large multi-site randomized study proposal |
| Secondary Objective | Provide insight into parental willingness for randomization regarding treatment interventions to be used |
| Research Intervention(s) / Investigational Agents | 1) Percutaneous (catheter-based) closure of patent ductus arteriosus [active intervention], 2) Conservative management of patent ductus arteriosus [non-intervention] 3) "Rescue" intervention (if medically necessary for conservative management group [rescue intervention]) |
| IND/IDE # | N/A |
| Study Population | Premature infants born at <28 weeks gestation with hemodynamically significant patent ductus arteriosus (PDA) at days of life 14 – 28. |
| Sample Size | 10 each for interventions 1) and 2) for a total of 20 enrolled at NCH. 20 additional infants will be enrolled at the collaborating institution (University of Tennessee Health Sciences Center) Unknown additional for non-randomized prospective data collection (see protocol narrative) |
| Study Duration for individual participants | From birth to hospital discharge. |
| Study Specific Abbreviations / Definitions | PDA ≡ patent ductus arteriosus; ECHO ≡ echocardiography; HSPDA ≡ hemodynamically-significant patent ductus arteriosus; NCH ≡ Nationwide Children's Hospital; UTHSC ≡ University of Tennessee Health Sciences Center |

2.0 Objectives

This pilot study is intended to collect preliminary data for a large, multi-site study proposal:

Percutaneous Intervention Versus Observational Trial of Arterial ductus in Low-weight infants (PIVOTAL). Not only will this pilot trial serve to collect preliminary data, but it will also provide critical information with regards to parental willingness to have their infants randomized to a particular intervention, which may affect recruitment strategies for a larger endeavor. The underlying hypothesis is that percutaneous closure will reduce the incidence and severity of bronchopulmonary dysplasia (BPD) in these infants, as evidenced by need for supplemental oxygen and ventilator support.

3.0 Background

PIVOTAL Pilot Study

Patent ductus arteriosus (PDA) is the most common cardiovascular complication among preterm infants, and there is ongoing debate regarding if intervention is required, when intervention is warranted or necessary, and how best to intervene. Treatment strategies for PDA vary markedly among institutions, with some centers aggressively pursuing intervention (closure), based on evidence that a PDA is associated with greater rates of mortality and linked to harmful longer-term outcomes, including chronic lung disease and heart failure. Other centers prefer a conservative approach, with no active intervention, in the hopes that the PDA will close naturally. This approach is based upon evidence that all forms of deliberate ductal closure have the potential for adverse side effects and that no studies have shown that treating all preterm infants with a PDA improves outcomes. These two very different approaches frame the ongoing debate and controversy regarding PDA patient management and treatment, and will form the two different treatment “arms” for the pilot study. Both the current, pilot study and the later multicenter trial will be centered around two widely accepted methods for treating PDA in preterm infants, both of which are considered “standard of care” at Nationwide Children’s Hospital (NCH). An additional item frequently debated among cardiologists and neonatologists is the definition of “Hemodynamically-significant” when it comes to PDA. To avoid confusion, we have elected to define a number of both clinical and echocardiographic criteria for evaluating whether or not a PDA would be considered “hemodynamically significant” (HSPDA). These criteria are shown in **Table 1**.

4.0 Study Endpoints

Discharge from the hospital.

5.0 Study Intervention/Investigational Agent

At NCH, the interventional method of choice is percutaneous (catheter-based) closure, in which a catheter is run to the heart and a device is implanted within the PDA of the patient in an effort to close it. Surgical ligation of the ductus is only performed at NCH under very unusual circumstances where catheter intervention is contraindicated. For the purposes of this study, the closure device that will be implanted is sized based upon measurements taken during the procedure. It is anticipated that most, if not all of the infants in this arm of the study will receive the Amplatzer Piccolo Occluder (formerly the Amplatzer Duct Occluder II Additional Sizes), which received FDA approval in January of this year. The second method is conservative

PIVOTAL Pilot Study

treatment (aka – “watchful waiting”), in which fluid intake is restricted and the patient is administered diuretic medications, but no physical intervention is applied in the hopes that the ductus will close naturally.

We recognize that parents may be reluctant to permit randomization to one treatment or the other (ie – leaving the treatment approach up to chance). For this reason, we have introduced a purely observational second “arm” to the study (**Figure 1**). Parent(s) who decline randomization, and therefore, enrollment in the randomized pilot trial will be given the option to approve prospective data collection, if they are willing to do so. A second consent document has been prepared for this purpose.

6.0 Procedures Involved

Echocardiography (ECHO): All possible participants will receive a research ECHO as a “qualifying” or “screening” step. This will occur at any point during the 14 – 28 postnatal day time period once informed consent for participation has been obtained. Patients meeting criteria for hemodynamic significance (**Table 1**) will qualify. Patients with a closed PDA or a PDA not meeting the criteria as hemodynamically-significant on this qualifying ECHO will be excluded from further participation. There will be an additional research ECHO performed at 36 weeks corrected gestational age. Additional echocardiographic studies during hospitalization will be at the discretion of the attending treatment team(s).

ECHO studies will be obtained via standard practice at NCH and UTHSC for neonatal subjects. Pre-warmed coupling gel will be placed on the chest of the subject, and the "wand" will be placed in contact with the chest under minimal pressure. The wand will then be carefully moved and positioned to obtain the appropriate viewing angles for optimum image and data acquisition. Clinical ECHOs from NCH will be stored on a secured server (EcholMS) for later analysis; research ECHOs will be stored initially on the secure Merge database. ECHO data and reports are currently scheduled to be moved to the secure Siemens Syngo system in July of 2019. ECHOs at UTHSC will be stored and analyzed per institutional protocol, but PHI will be removed from ECHO reports prior to sharing with NCH (see *Data Sharing Between External Entities*).

Percutaneous PDA Closure:

Briefly, femoral venous access will be used exclusively. A coronary guidewire will be advanced under fluoroscopic guidance through the right heart, across the PDA, and into an ileac artery. A 4-F hydrophilic sheath (Flexor, Cook Medical, Bloomington, Indiana) will be advanced over the

PIVOTAL Pilot Study

wire into the descending aorta, and the ADO-II AS device implanted through the sheath using a combination of fluoroscopic and echocardiographic guidance. Prior to release from the delivery cable, the left pulmonary artery (LPA) and descending aorta will be carefully evaluated by echocardiography with 2-dimensional imaging and color and spectral Doppler and compared with the pre-procedural imaging. If vascular stenosis related to the device is observed, as defined by a maximal instantaneous gradient >15 mm Hg or an “obstructed” pattern with persistent antegrade diastolic flow, the device will be recaptured and either repositioned or removed and replaced with another device of a different size. If on repeat attempt(s) there was persistent stenosis, the patient was converted to surgical ligation. Following release of the device, echocardiographic evaluation of all pertinent structures will be repeated. Per protocol, patients will be administered a single intraprocedural and 2 post-procedural doses of antibiotics (cefazolin 25 mg/kg) and a single procedural dose of intravenous heparin (100 U/kg) unless contraindicated.

Conservative Treatment: For this approach, both medication (primarily diuretics) and fluid restriction may be used in the hopes of limiting PDA-related complications while allowing time for natural closure. Under this protocol, healthcare decisions will be made at the discretion of the treatment team, while the infant is carefully monitored for any decline in status that may be attributed to the presence of PDA. In this case, “Rescue” Intervention (below) may be considered.

“Rescue” Intervention: It is recognized that some infants randomized to the conservative management arm will continue to have a HSPDA, which may be hindering clinical improvement or worse yet, be an underlying or secondary cause for continued clinical decline. If deemed medically necessary by the treating physicians, and additional criteria are met, these infants will be assigned to “Rescue” intervention by percutaneous closure. These “additional” criteria are noted below (*please refer to Table 1, also*):

RESCUE CRITERIA #1

- Receipt of dopamine or dobutamine at ≥ 10 mcg/kg/minute or epinephrine or norepinephrine at ≥ 0.01 mcg/kg/min for systemic hypoperfusion, as determined by attending Neonatologist in the absence of non-PDA related etiologies
- OR
- Increase in $\text{FiO}_2 >20\%$ from baseline value for >24 hours in the absence of atelectasis or worsening interstitial lung disease
- OR

PIVOTAL Pilot Study

- Increase in baseline creatinine >30% *and* creatinine >1 mg/dL
- AND
- ≥3 large ECHO criteria
- ≥1 large ECHO criteria AND mitral regurgitation (annular dilatation of the valve)

RESCUE CRITERIA #2

- Moderate OR severe clinical criteria AND ≥1 criteria for large ECHO criteria
- AND
- mitral regurgitation (annular dilatation of the valve)

Data to be Collected: Clinical echocardiographic data for NCH-enrolled patients will be obtained from ECHO reports on the EchoIMS server. Research ECHO data will be stored initially on the secure Merge database. ECHO data and reports are currently scheduled to be moved to the secure Siemens Syngo system in July of 2019. Catheterization data (Percutaneous intervention arm) and information will be obtained from the reports found under the “Cardiology” tab in EPIC. All other data will be obtained from the patient’s electronic medical record. Data collected at UTHSC will similarly involve the patient’s electronic medical records, and ECHO data retrieved from local, secure databases, if not embedded within the medical records.

Demographics (Patient): Date of birth, Gender, Gestational age, Birth weight, Birth length, Weight and length at procedure (if applicable), Study arm assignment

Echocardiographic (ECHO): Date of ECHO study, Results of ECHO studies - including all cardiac and major blood vessel measurements and performance evaluations, PDA size, PDA flow direction (All clinical ECHO studies, as well as research-specific ECHO studies), and any ECHO contraindications for percutaneous closure

Procedural (Percutaneous closure arm): Date of procedure, Type of implant / device used, Number of implant attempts, Procedural complications, Time of procedure start, Time of procedure end, Medications and anesthetics administered, fluoroscopic data (contrast dose, timing), receipt of transfusion (if applicable), Post-operative complications (if applicable), All hemodynamic measurements obtained – including size and type of PDA per angiography, Any catheter-based finding that would contraindicate percutaneous closure (ex – previously

PIVOTAL Pilot Study

undiagnosed aortic coarctation or narrowing of the left pulmonary artery), Any adverse events reported

Conservative treatment arm: Medication(s) administered (with focus upon diuretics), Doses of medications, Date(s) of medications, Fluid intake restriction volumes, Referral(s) for percutaneous closure and procedural data as noted above (if applicable, for “Rescue” cases)

Hospitalization: Date of admission, Diagnosis and severity of known preterm morbidities (necrotizing enterocolitis, intraventricular hemorrhage, retinopathy of prematurity, bronchopulmonary dysplasia), Body weight, Length/Height, Treatment with supplemental oxygen – including dates, ventilatory support, and % oxygen, Dates on IV fluids, Date of full PO intake, Date of discharge, Length of stay

7.0 Data and Specimen Banking

Clinical data will be kept on the secure and limited-access patient database at Nationwide Children’s Hospital, EPIC for NCH patients. Clinical echocardiography scans and reports will be stored on a secure and limited-access database, EchoIMS. Research ECHO data will be stored initially on the secure Merge database, but are currently scheduled to be moved to the secure Siemens Syngo system in July of 2019. Data that is collected at NCH for analysis from these sources will be stored on secure, limited-access shared storage locations (R:) as Excel files. Clinical and ECHO data collected at UTHSC will be stored in accordance to local protocols. PHI will be removed from UTHSC-collected data and ECHO reports prior to sharing with NCH (see *Data Sharing Between External Entities*). No specimens will be collected and stored for this study.

8.0 Sharing of Results with Subjects

The procedural outcomes for the infants in the percutaneous intervention arm will be shared with the parents, either by the interventional cardiologist or a representative. The parents of infants in the conservative management arm will likewise be aware of the outcomes, as the PDA will either be 1) open at discharge – requiring Cardiology follow up, or 2) closed at discharge – not requiring Cardiology follow-up. Similarly, infants who qualify for Rescue Intervention will be consulted regarding the procedure, as consent to perform said procedure (including discussion

PIVOTAL Pilot Study

of risks) must be obtained prior to the intervention, and the outcomes of the procedure discussed as previously noted. The procedural reports will be placed in the patient's electronic medical record, which may be shared at a later date with a patient's primary care physician, if requested. Pilot study results will be posted on ClinicalTrials.gov.

9.0 Study Timelines

Prior to 14 days postnatal, up to 28 postnatal days of age: Obtain informed consent / informed consent process

14 – 28 postnatal days of age: Qualifying ECHO and randomization (if permitted) for all patients that qualify for participation in the study.

Within 72 hours of randomization (Percutaneous arm ONLY): Catheter-based closure of PDA

Otherwise (Conservative arm ONLY): Treatment per institutional guidelines for conservative management of PDA

Continuous: Data collection on clinical status, including clinical ECHO studies, ventilatory support, need for supplemental oxygen, and other complications. For Conservative arm ONLY – clinical and treatment team evaluations to determine if Rescue Intervention is warranted.

36 weeks corrected gestational age: Follow-up ECHO study.

Discharge: Study exit; if randomized to conservative arm and no Rescue Intervention is required, status of PDA (open / closed) and size, if known at time of discharge.

Post-Discharge analysis: 1 year after discharge of the final patient enrolled to either the percutaneous intervention arm OR conservative management arm (based upon randomization order; it is currently unknown which treatment the final randomized patient will be assigned to).

10.0 Inclusion and Exclusion Criteria

Study Inclusion Criteria:

1. Premature infants born at <28 weeks gestation
2. HSPDA (criteria, **Table 1**) verified by treating cardiologist and echocardiographic imaging

Study Exclusion Criteria:

PIVOTAL Pilot Study

1. Patients meeting criteria initially, but with a non-hemodynamically-significant PDA or closed PDA at postnatal age of 14 days (ex. – a patient with a large PDA and echocardiographic signs of fluid overload and/or cardiac remodeling at day of life 7, which decreased in size to small with a reduction in symptomology by day of life 14)
2. Life-threatening congenital abnormalities, including congenital heart disease (excluding patent ductus arteriosus and atrial septal defects (ASDs) / ventricular septal defects (VSDs)). Infants with evidence of coarctation of the aorta or left pulmonary artery stenosis will be excluded
3. Infants with evidence of pulmonary hypertension, as defined by ductal right to left shunting for more than 33% of the cardiac cycle.
4. Infants likely to require surgical treatment (ex. – congenital diaphragmatic hernia, omphalocele, gastroschisis), abnormalities of the upper and lower airways (Pierre-Robin sequence, pulmonary hypoplasia), and neuromuscular disorders.
5. Infants for whom treatment withdrawal or limitation of intensive care treatment is being considered.

11.0 Vulnerable Populations

This research involves children (neonates) who are not of legal age to provide informed consent themselves. Thus, the parent(s) of the patients will be approached to obtain informed consent for their child or children (in the case of multiple gestation infants) to participate. Regarding cases of uncertain viability of neonates, as noted above, infants for whom treatment withdrawal or limitation is considered or mandated will be excluded from participation in the study.

12.0 Number of Subjects

The objective is to have 10 subjects per treatment arm (Percutaneous closure, Conservative management) for a total of 20 in the randomized intervention study. An additional 20 patients (10 per treatment arm) will be recruited at the University of Tennessee Health Sciences Center. The number of non-randomized, prospective data collection participants remains uncertain, and cannot be predicted.

13.0 Recruitment Methods

PIVOTAL Pilot Study

Potential participants will be identified from the neonatal intensive care unit (NICU) patient pool at Nationwide Children's Hospital, Main Campus and similarly at The University of Tennessee Health Sciences Center. Potential subjects will include all infants born at <28 weeks who do not meet any of the exclusion criteria. This will include infants with a previously-identified, open PDA on a clinical echocardiography (ECHO) study, or infants who have had no ECHO study performed prior to transfer to NCH or UTHSC. Parental informed consent will be obtained prior to a qualifying echocardiography study being performed. Face-to-face contact will be the primary method; however, telephone consents will be allowed for cases in which an infant was transferred from an outside institution and the parents are otherwise unavailable. During the consenting process, the randomized nature of the study interventions will be clearly defined. Parents who express a preference to one specific option, or are uncomfortable with the idea of randomization will be excluded from the randomized trial, and will be asked to provide consent for prospective data collection only. A second consent form has been prepared for this purpose.

14.0 Withdrawal of Subjects

Subjects will be free to withdraw from the study at any time. Additionally, subjects may be excluded / withdrawn by the study team if previously undiagnosed conditions are found after consent has been obtained (ex. – a previously undiagnosed aortic coarctation, which is a contraindication to percutaneous closure).

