Patients and their parent(s) will be afforded privacy in accordance with NCH and UTHSC standards for care. Contact with the parent(s) will be required in order to obtain consent. They will be asked by consenting personnel if they are open to the idea of having their child participate in a research study. Further contact would only be if they were willing to consider it or for further discussion during the process. Those that refuse will no longer be approached. Follow up for those who are "thinking about it" or "considering it" will be limited, as well. Additional contact with the parent(s) will be required prior to the interventional procedure (for patients randomized to the percutaneous intervention arm), in order to obtain consent for said procedure. This will be done by a member of the interventional cardiology team.

PIVOTAL Pilot Study

The qualifying ECHO scan is a research-specific scan, separate from any that would otherwise be performed for clinical purposes, and is recognized as an additional instance in which contact with the infant occurs, but is necessary for the purposes of the study to ensure that appropriate inclusion criteria are met, and that exclusion criteria are not present. This would include findings of non-hemodynamically-significant PDA, for which intervention would not be warranted.

All data obtained through the study will be stored in either a locked file in the research office (paper consent forms) or stored on a secured shared drive accessible only by password-protected computer systems behind the NCH firewall. Similar data security practices are in place at UTHSC. Prior to sharing data, PHI will be removed from data sources at NCH and UTHSC. Generic “identifiers” will be used for each case (“1”, “2”, “3”) in place of names and/or MRNs. (see *Data Sharing Between External Entities*).

Confidential Health Information

1.0 Please mark all categories that reflect the nature of health information to be accessed and used as part of this research.

- Demographics (age, gender, educational level)
- Diagnosis
- Laboratory reports
- Radiology reports
- Discharge summaries
- Procedures/Treatments received
- Dates related to course of treatment (admission, surgery, discharge)
- Billing information
- Names of drugs and/or devices used as part of treatment
- Location of treatment
- Name of treatment provider
- Surgical reports
- Other information related to course of treatment
- None

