| | 
**Composite risk of death or moderate or severe BPD must be $> 50\%$ (Laughon et al. Prediction of Bronchopulmonary Dysplasia by Postnatal Age in Extremely Premature Infants. Am J Respir Crit Care Med. 2011)
 | | | | | | |
| 
DA= Descending aorta; LVO= Left ventricular output will be calculated as follows: $[(\text{Velocity time integral}) \times (\text{Heart rate}) \times (\text{Aortic cross-sectional area})]$ indexed to body weight
 | | | | | | | |

Figure 1: PIVOTAL pilot trial flowsheet

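### Section 14 lets the study team withdraw infants for conditions found after consent, with no cut-off at randomization, although catheterization, which can reveal such conditions, is routine only in the closure arm

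*Combined protocol and SAP*

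**What the plan says.** Section 14.0 (Withdrawal of Subjects) provides that "subjects may be excluded / withdrawn by the study team if previously undiagnosed conditions are found after consent has been obtained". Its example is an undiagnosed aortic coarctation, described as a contraindication to percutaneous closure. The power starts at consent, and no end is given.

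Other sections fix the order of events and the imaging each arm receives:

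- Section 13.0 places parental consent before the qualifying ECHO. Section 9.0 puts that ECHO and randomization at postnatal days 14 to 28.
- Section 10.0 makes the same lesion an entry exclusion: "Infants with evidence of coarctation of the aorta or left pulmonary artery stenosis will be excluded". Section 27.0 (item 6.0, privacy) says the qualifying ECHO serves in part to ensure "that exclusion criteria are not present".
- Section 9.0 then schedules "Within 72 hours of randomization (Percutaneous arm ONLY): Catheter-based closure of PDA".
- Section 6.0, in the procedural data for the closure arm, lists "Any catheter-based finding that would contraindicate percutaneous closure", with undiagnosed coarctation and left pulmonary artery narrowing as examples. It also describes ECHO assessment of the left pulmonary artery and descending aorta during the procedure.
- For the conservative arm, Section 6.0 collects "Referral(s) for percutaneous closure and procedural data as noted above" for rescue cases only.
- For both arms, Section 6.0 states: "There will be an additional research ECHO performed at 36 weeks corrected gestational age". Other ECHOs are at the treating team's discretion.

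No available passage says that an infant withdrawn after randomization stays in data collection or is counted in the assigned arm.

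**The concern.** Randomization makes the arms comparable only if the infants who leave afterwards do so for reasons that operate alike in both arms. Here the reason is a newly found condition, and one arm is looked at more closely and sooner. An infant with a missed coarctation may be found and removed in the closure arm, while a similar infant in the conservative arm goes undetected and stays. The decision is also discretionary, and no blinding of it is described.

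Two things are at stake in a pilot meant to supply preliminary data for a larger randomized trial. One is the comparison of BPD, oxygen and ventilator outcomes between arms. The documents do not say how such infants fare, so the direction of any distortion is unknown. The other is the share of infants assigned to closure who can actually receive it. If infants who could not have closure leave the denominator, that share is overstated, and a larger trial planned on it would expect too few infants to miss their assigned treatment.

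**Working it through.** The protocol states no event rate, power calculation or rate of missed contraindications, so there is no figure of its own to reproduce beyond the counts.

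**Does the rule reach past randomization?** Consent comes first, then the qualifying ECHO, then randomization, then catheterization within 72 hours in the closure arm. The withdrawal power opens at the first step and is not closed at any later one. Section 14's example is the same lesion that Section 6.0 lists as a possible finding at catheterization, which happens after randomization. The post-randomization use is therefore one that the protocol's own data list foresees.

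**Is detection unequal?** In the closure arm, catheterization and intraprocedural ECHO are routine. In the conservative arm, catheterization occurs only on rescue. Clinical ECHOs and the 36-week ECHO can reveal lesions in either arm, so removal is possible in both but more likely in the closure arm.

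**Inputs.**
- Arm size, from Section 12.0: 10 per arm at each of two sites, so n = 10 + 10 = 20 per arm.
- Closure infants removed: k = 1, 2 or 3 (assumption).
- Event rate: 60%, range 50% to 70% (assumption). The only anchor is the Table 1 footnote, "Composite risk of death or moderate or severe BPD must be" above 50%, for its marked categories. That is an eligibility threshold on predicted risk, not a forecast rate.

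**How often might it happen?** If a share c of infants has a missed contraindication and all are found at catheterization, the chance of at least one in 20 is 1 − (1 − c)^20. For assumed c = 2.5%, 5% and 10% this is 40%, 64% and 88%, with 0.5, 1 and 2 infants expected.

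**Shift in the closure-arm event rate.** Before removal there are 12/20 = 60% events.

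| Removed infants | Formula | k = 1 | k = 2 | k = 3 |
|---|---|---|---|---|
| All had the event | (12 − k)/(20 − k) | 57.9% (−2.1) | 55.6% (−4.4) | 52.9% (−7.1) |
| Risk 80% | (12 − 0.8k)/(20 − k) | −1.1 | −2.2 | −3.5 |
| Risk 60% | (12 − 0.6k)/(20 − k) | 0 | 0 | 0 |
| Risk 40% | (12 − 0.4k)/(20 − k) | +1.1 | +2.2 | +3.5 |
| None had the event | 12/(20 − k) | 63.2% (+3.2) | 66.7% (+6.7) | 70.6% (+10.6) |

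Shifts are in percentage points. With k = 3, a 50% base rate gives 7/17 = 41.2% (−8.8) to 10/17 = 58.8% (+8.8). A 70% base rate gives 11/17 = 64.7% (−5.3) to 14/17 = 82.4% (+12.4).

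**Against sampling error.** The standard error of the difference between arms at 60% is √(2 × 0.6 × 0.4/20) = 15.5 points. At 50% it is √(2 × 0.5 × 0.5/20) = 15.8, and at 70% it is √(2 × 0.7 × 0.3/20) = 14.5. Every shift above is below one standard error at its own base rate.

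**Feasibility.** If closure is done in all other infants, it is done in (20 − k)/(20 − k) = 100% of those remaining, against (20 − k)/20 = 95%, 90% or 85% of those assigned. If some other closures also fail, so that m are done, the two figures are m/(20 − k) and m/20. Their ratio is 20/(20 − k) = 1.05, 1.11 or 1.18 whatever m is.

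**The case against.** The strongest reply is that Section 14 describes screening. Consent precedes the qualifying ECHO, that ECHO checks the exclusions, and coarctation is one of them, so removal after consent fits an ordinary screen failure. The word *may* also leaves removal optional. This is a fair reading of part of the rule, but the sentence is not limited to screening, and Section 6.0 expects the same lesion to turn up at catheterization.

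Several further points stand as limits:

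- With a screening ECHO in place such cases should be uncommon. Three in 20 would mean 15% missed, which nothing in the documents supports.
- The largest outcome shifts need all or none of the removed infants to have the event. At average risk the expected shift is zero.
- Section 6.0 already collects study arm and the contraindicating finding, so the feasibility count could be built. What is missing is a commitment to report it over all infants assigned.
- Only infants with newly found conditions could leave the denominator. Section 6.0 describes conversion to surgical ligation for persistent stenosis and does not call it withdrawal.
- The protocol describes no test between arms and does not anticipate significant biostatistical analysis, so the missing assigned-arm rule is partly a consequence of having no analysis plan. The parental-willingness objective is unaffected.
- Figure 1 and the consent pages could not be read, so the statement that nothing retains these infants applies to the available text.

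These points reduce the expected size. They do not close the gap, because following Section 14 as written can still drop randomized infants on arm-dependent information.

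**Conclusion.** The concern holds and should be fixed. That the rule runs past randomization, and that routine catheterization is confined to one arm, both follow directly from the text. How often it would matter is unknown.

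For outcomes, no direction can be claimed. Under the stated assumptions the extreme shifts are −7.1 to +10.6 points at a 60% event rate with up to three of 20 removed, and 1.1 to 3.5 points either way if the removed infants' risk differs from the arm average by 20 points. This would not dominate a pilot of 20 per arm, but it is an avoidable distortion of the preliminary estimates.

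For feasibility, the direction is known: the share of assigned infants who receive closure is overstated by a factor of 1.05 to 1.18 for one to three removals. This assumes that the removed infants did not have closure and are left out of the denominator.

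**What to change.** Amend Section 14.0 so that exclusion by the study team for newly found conditions ends at randomization. Screen failures at or before the qualifying ECHO stay allowed. Then add wording such as:

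> An infant in either arm in whom any previously undiagnosed condition is found after randomization, including a contraindication to closure, remains in data collection to discharge and is analysed in the arm assigned. Care is decided by the treating team. Parents' right to withdraw is unchanged.

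The wording should cover any newly found condition, because Section 14 is not limited to contraindications to closure.

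Also commit to reporting the number of infants assigned to closure in whom it was not done, with reasons, over all infants assigned. Section 6.0 already collects the contraindicating finding.

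The cost is two or three sentences and one reported count. No new data are needed, since the infants are in hospital and their records are already being read to discharge. The downside is that the closure-arm estimate will include some infants who did not receive closure, which a comparison by assigned arm requires. The change concerns who is followed and counted, and leaves clinical management as it is.
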